CLINICAL STUDY PROTOCOL

Arrhythmia Burden in Patients with Impulse Dynamics Optimizer Smart Device Implantation: Retrospective and Prospective Evaluation

Protocol Version
12/23/2022

version 1.0

| | |
|--------------|------------|
| Study Number | 12/20/2022 |
|--------------|------------|

Study Authors

[name]

Lead Study Principal Investigator: [name]

Hackensack University Medical Center,

Hackensack Meridian School of Medicine

Abbreviations

| Abbreviation | Explanation |
|--------------|-------------|
|--------------|-------------|

AF=Atrial fibrillation

CCM= Cardiac Contractility Modulation

CHF=congestive heart failure

CIED= cardiovascular implantable electronic device

FDA=Food and Drug Administration

HFrEF=heart failure with reduced ejection fraction

ICD=Internal Cardioverter Defibrillator

ILR=implantable loop recorder

PPM=Permanent pacemaker

LVEF=left ventricular ejection fraction

NYHA>New York Heart Association

VA=Ventricular arrhythmia

VF=Ventricular fibrillation

VT=Ventricular tachycardia

| | |
|--------------|------------|
| Study Number | 12/20/2022 |
|--------------|------------|

Summary

The Impulse Dynamics Optimizer Device is a Food and Drug Administration (FDA) approved, commercially available device indicated for patients with heart failure with reduced ejection fraction (HFrEF), currently being implanted per FDA recommendation. Many candidates of this device have a previously implanted cardiovascular implantable electronic device (CIED)- internal cardioverter defibrillator (ICD) or permanent pacemaker (PM). Patients with heart failure are at high risk for both atrial and ventricular cardiac arrhythmias.

The aim of this study is to evaluate up to 200 patients for Atrial fibrillation (AF) burden episode data obtained from interrogation of their CIED 8 months or greater after Optimizer implant, and compare arrhythmia burden 6 months before Optimizer Cardiac Contractility Modulation (CCM) device insertion to 6 months or greater after Optimizer insertion, after an immediate implantation blanking period of 2 months.

| | |
|--------------|------------|
| Study Number | 12/20/2022 |
|--------------|------------|

1 – Introduction

The Impulse Dynamics Optimizer is indicated for patients with New York Heart Association (NYHA) class III congestive heart failure (CHF) with left ventricular ejection fraction (LVEF) between 25 and 45% who are not candidates for cardiac resynchronization therapy. The Optimizer device requires a minimally invasive implant by a cardiac electrophysiologist with two transvenous pacemaker wires implanted into the right ventricular septum and attached to a generator in an infraclavicular region, much like a pacemaker. The Optimizer device provides CCM through improved calcium handling and has been shown to reverse the negative remodeling of the left ventricle seen in HFrEF and improve left ventricular contractile strength.

We plan to enroll a maximum of 200 patients with existing or newly implanted Impulse Dynamics Optimizer with concurrent previously implanted CIED.

2 – Background

AF demonstrates an average prevalence of 25% in HFrEF, and is the most common sustained arrhythmia encountered in the HFrEF population (1). AF burden in HFrEF is estimated at 35%. AF increases risks of CHF hospitalizations and mortality in HFrEF (2). Episodes of AF longer than 24 hours in a non HFrEF population substantially increased risk of stroke (3). Sudden cardiac death, most often a result of ventricular arrhythmia (VA), accounts for 30-50% of the deaths in heart failure patients (4-5). CCM is a novel therapy for patients with heart failure with a variety of short and long-term benefits. While CCM has been shown to improve health status and reduce hospitalization rates in those with AF (6), there is a paucity of data examining the impact of CCM therapy on arrhythmia burden.

3 – Rationale, Objectives and Hypothesis

3.1 Study Rationale

There are no studies that assess the impact of the Optimizer device on atrial and ventricular arrhythmias, and any investigation is unique and may add value. The study will be performed in two arms. The first arm will be retrospective and the second arm will be prospective. We will perform a retrospective review of atrial and ventricular arrhythmias that occur 6 months before and 8 months after the Optimizer device is implanted in patients with a CIED with the ability to interpret atrial signals. The 8 months post implant period will include a 2 month blanking period which will allow for the therapeutic effects of CCM. Patients who have undergone Optimizer implantation, but do not have at least 8 months of follow up, can be enrolled in the retrospective arm and signed informed consent will be required. The prospective arm will include patients who have had a CIED with the ability to interpret atrial signals for at least 6 months and have a clinical indication for CCM therapy as per standard of care. These patients will be followed for 8 months post Optimizer implant, including an initial 2 month post Optimizer implant blanking period.

3.2 Hypothesis

We hypothesize that treatment with Optimizer will result in a 20% reduction of AF burden.

| | |
|--------------|------------|
| Study Number | 12/20/2022 |
|--------------|------------|

3.3 Primary Objective

The primary objective for both the retrospective and prospective arms of the study is to compare the AF burden noted 6 months pre Optimizer implant to 6 post Optimizer months (post Optimizer months 3-8), after 2 month blanking period

3.4 Exploratory Objectives

All exploratory objectives will be performed for both retrospective and prospective arms separately and together with comparisons to be made between the following groups:

1. 6 months pre Optimizer to 6 post Optimizer months (post Optimizer months 3-8), after 2 month blanking period
2. 6 months pre Optimizer to 6 post Optimizer months (post Optimizer months 1-6)
3. 3 months pre Optimizer to 3 post Optimizer months (post Optimizer months 3-5), after 2 month blanking period
4. 3 months pre Optimizer to 3 post Optimizer months (post Optimizer months 6-8), after 2 month blanking period
5. 3 months pre Optimizer to 3 post Optimizer months (post Optimizer months 1-3)
6. 3 months pre Optimizer to 3 post Optimizer months (post Optimizer months 4-6)

3.4.1 Exploratory Objective One

Exploratory objective one is to compare the AF burden between groups 2-6 noted above.

3.4.2 Exploratory Objective Two

Exploratory objective two is to compare the number of VA episodes between all groups noted above.

3.4.3 Exploratory Objective Three

Exploratory objective three is to compare the AF burden after censoring subjects who underwent cardioversion or catheter ablation of AF during entire study period between all groups noted above.

3.4.4 Exploratory Objective Four

Exploratory objective four is to compare the AF burden after censoring subjects who had addition of antiarrhythmic drug, underwent cardioversion, or underwent catheter ablation during entire study period between all groups noted above.

3.4.5 Exploratory Objective Five

Exploratory objective five is to compare the number of hospitalizations between all groups noted above.

3.4.6 Exploratory Objective Six

Exploratory objective six is to compare the number of stroke events between all groups noted above.

3.4.7 Exploratory Objective Seven

| | |
|--------------|------------|
| Study Number | 12/20/2022 |
|--------------|------------|

Exploratory objective seven is to compare the number of catheter ablations between all groups noted above.

3.4.8 Exploratory Objective Eight

Exploratory objective eight is to compare the number of cardioversions between all groups noted above.

3.4.9 Exploratory Objective Nine

Exploratory objective nine is to compare the number of AF events \geq 24 hours between all groups noted above.

4 - Study Design

4.1 General Design

The study will be conducted in two arms. The retrospective arm will be an observational evaluation of subjects with a CIED with the ability to interpret atrial signals implanted at least 6 months prior to Optimizer implantation. Additionally, these subjects will be at least 8 months post Optimizer implant at the time of study approval. Subjects with an appropriate CIED and who have undergone Optimizer implantation, but do not have at least 8 months of post Optimizer implantation follow up, can be enrolled in the retrospective arm, but signed informed consent will be required.

The prospective arm will be an observational evaluation of subjects with an appropriate CIED implanted at least 6 months prior and scheduled to undergo Optimizer implantation as per standard of care. Informed consent will be obtained from all subjects in the prospective arm at a recommended time of 2-4 weeks before scheduled Optimizer implant date. A CIED interrogation (remote or in-person) is to be performed 2-4 weeks prior to Optimizer implant date as per standard of care. If AF burden is noted to be between 1% and 99% (reported for any time equal to or less than the prior 6 month period), the patient can be enrolled into the prospective arm of the study. Arrhythmia burden data from the CIED manufacturer will also be requested; if this data does not corroborate AF burden between 1% and 99% then the patient will be considered a screen failure. AF burden and VA episodes will be assessed remotely through the CIED manufacturer and compared from the pre implantation period to the post implantation period, as defined above. The prospective arm will allow attainment of information prospectively during 8 months of follow up after Optimizer implantation, including an initial 2 month post Optimizer implant blanking period.

Evaluation for both arms will include:

1. Pre-6 months to Optimizer implant (will be subcategorized into pre-6 to pre-3 months, and pre-3 months to Optimizer implant)
2. Optimizer implant date to post-8 months [will be subcategorized into Optimizer implant to post 2 months (blanking period), post-2 months to post-5 months, and post-5 months to post-8 months], and if applicable every 3 months thereafter.

| | |
|--------------|------------|
| Study Number | 12/20/2022 |
|--------------|------------|

In terms of arrhythmia reporting, AF burden will be reported as (1) hours of AF/day (2) percent AF per day and (3) number of AF episodes \geq 24 hours/1 month period, including in the 2 month blanking period.

VA episodes will be categorized into types and number of events as reported by the CIED as (1) treated VT and treated VF together and (2) untreated non-sustained VT, treated VT, and treated VF together.

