4.3 Study procedures

AF burden and VT episodes will be remotely accessed from the CIED manufacturer. The prospective arm will allow prospective data collection for 8 months after Optimizer implantation, including a 2 month blanking period immediately after Optimizer implantation.

For the retrospective and the prospective arms, the data will be evaluated in the same manner, except as noted below, and will be performed as follows:

1. Pre-6 months to Optimizer implant (will be subcategorized into pre-6 to pre-3 months, and pre-3 months to Optimizer implant), to ensure $1\% \leq \text{AF burden} \leq 99\%$ (otherwise subjects will be excluded).
2. Optimizer implant date will be followed by a 60 day blanking period. The patients will be followed for 8 months [will be subcategorized into Optimizer implant to post-2 months (blanking period), post-2 month blanking period to post-5 months, and post-5 months to post-8 months, and every 3 months thereafter until the study is completed).

AF burden will be reported as (1) hours of AF/day (2) percent AF per day and (3) number of AF episodes ≥ 24 hours/1 month period, including the blanking period.

Demographics, development of medical events (hospitalization, stroke) and arrhythmia related history (presence/absence of medications) and interventions, such as cardioversion, antiarrhythmic drug administration, or catheter ablation will be recorded.

VA episodes will be categorized into types and number of events as reported by the CIED as (1) treated VT and treated VF together and (2) untreated non-sustained VT, treated VT, and treated VF together.

| | |
|--------------|------------|
| Study Number | 12/20/2022 |
|--------------|------------|

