5.3.2 Statistical Methods for Exploratory Objectives

All exploratory objectives will be performed for both retrospective and prospective arms separately and together with comparisons to be made between the following groups:

1. 6 months pre Optimizer to 6 post Optimizer months (post Optimizer months 3-8), after 2 month blanking period
2. 6 months pre Optimizer to 6 post Optimizer months (post Optimizer months 1-6)
3. 3 months pre Optimizer to 3 post Optimizer months (post Optimizer months 3-5), after 2 month blanking period
4. 3 months pre Optimizer to 3 post Optimizer months (post Optimizer months 6-8), after 2 month blanking period
5. 3 months pre Optimizer to 3 post Optimizer months (post Optimizer months 1-3)
6. 3 months pre Optimizer to 3 post Optimizer months (post Optimizer months 4-6)

Exploratory objective one is to compare the AF burden between groups 2-6 noted above.

Exploratory objective two is to compare the number of VA episodes between all groups noted above.

Exploratory objective three is to compare the AF burden after censoring subjects who underwent cardioversion or catheter ablation of AF during entire study period between all groups noted above.

Exploratory objective four is to compare the AF burden after censoring subjects who had addition of antiarrhythmic drug, underwent cardioversion, or underwent catheter ablation during entire study period between all groups noted above.

Exploratory objective five is to compare the number of hospitalizations between all groups noted above.

Exploratory objective six is to compare the number of stroke events between all groups noted above.

| | |
|--------------|------------|
| Study Number | 12/20/2022 |
|--------------|------------|

Exploratory objective seven is to compare the number of catheter ablations between all groups noted above.

Exploratory objective eight is to compare the number of cardioversions between all groups noted above.

Exploratory objective nine is to compare the number of AF events ≥ 24 hours between all groups noted above.

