A patient's AF burden is measured as the cumulative time spent in AF over the assessment period divided by the cumulative follow-up time of the assessment period. The difference in AF burden between the post-Optimizer and pre-Optimizer AF assessment periods will be analyzed as a continuous variable. Visual inspection of q-q plots for skewness and outliers along with the Shapiro-Wilk test ($p>0.05$ indicates no deviation from normality and $p<0.05$ indicates deviation from normality) will be used to evaluate normality. If the distribution of changes in AF burden is approximately normally distributed, a paired t-test will be used for analysis and the mean, standard deviation, and range will be reported. Otherwise, if the distribution is non-normal, a Wilcoxon signed-rank test will be performed and the median, interquartile range, and range will be reported.

VA episode counts will be tabulated for the pre-Optimizer and post-Optimizer assessment periods. A Poisson generalized estimating equation (GEE) analysis accounting for clustering of paired counts within subject may be performed to compare the rate of VA episodes between the pre-Optimizer and post-Optimizer assessment periods.

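### The two ventricular arrhythmia counts include untreated non-sustained VT but omit sustained VT and VF that the device records without treating (minor; one exploratory objective)

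*Combined protocol and SAP*

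**What the plan says.** Section 4.1 (arrhythmia reporting) has VA episodes sorted by type and number "as reported by the CIED as (1) treated VT and treated VF together and (2) untreated non-sustained VT, treated VT, and treated VF together". Section 4.3 repeats the same two categories.

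The retrieval sentences differ. Section 4.1 has "AF burden and VA episodes will be assessed remotely through the CIED manufacturer"; section 4.3 has "AF burden and VT episodes will be remotely accessed from the CIED manufacturer".

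The objective served is 3.4.2, which is to "compare the number of VA episodes between all groups noted above"; section 5.3.2 restates it. For the analysis, 5.3.2 commits to this: "VA episode counts will be tabulated for the pre-Optimizer and post-Optimizer assessment periods". It then allows, but does not require, a Poisson GEE comparison of rates. Section 3.4 sets the scope: "All exploratory objectives will be performed for both retrospective and prospective arms separately and together", over six pairs of pre and post periods.

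Inclusion criterion 4 in section 4.2.3 admits a dual chamber pacemaker or an ICD. Section 3.1 describes the retrospective work as a "retrospective review of atrial and ventricular arrhythmias that occur 6 months before and 8 months after the Optimizer device is implanted", with no restriction to treated or non-sustained episodes.

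**The concern.** The broader category is the only place where an untreated episode can be counted, and the only untreated rhythm it names is non-sustained VT. A brief run that ends by itself is counted. A longer VT, or a VF, that the device logs without delivering therapy is not. Section 2 (Background) motivates the interest in VA by sudden cardiac death, so the omitted episodes are close to what the objective is about.

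Whether a sustained episode enters the count depends on whether the device treated it. Whether an untreated VT enters depends on its being short. If either feature shifts between the pre and post periods, the reported VA count moves although the number of arrhythmias has not. A reader of the final table could not see this, because nothing in the two categories shows how many episodes were left out.

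**Working it through.** The plan states no figure on this point, so there is none to reproduce. The check is a mapping, followed by algebra on assumed shares.

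**1. Mapping rhythm and therapy to the categories in 4.1 and 4.3**

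| Episode recorded by the device | Category 1 | Category 2 |
|---|---|---|
| Treated VT | yes | yes |
| Treated VF | yes | yes |
| Untreated non-sustained VT | no | yes |
| Untreated sustained VT | no | no |
| Untreated VF | no | no |

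Sections 3.4.2 and 5.3.2 speak only of VA episodes or VA episode counts. They add no definition and no residual category, so the last two rows stay empty.

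**2. Subjects whose device gives no VT/VF therapy.** Every VT or VF episode is then untreated. Category 1 is 0 in both periods whatever happens, and category 2 reduces to non-sustained VT. The documents do not give the pacemaker/ICD mix.

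**3. Effect on the post/pre ratio.** Let T be all recorded VT/VF episodes in a period, and s the share of T that is untreated and either sustained VT or VF. The category 2 count is T(1 - s), so

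category 2 ratio = (T_post / T_pre) × (1 - s_post) / (1 - s_pre).

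If s_post = s_pre, the second factor is 1 and the ratio is unbiased for all episodes. Otherwise it errs upward when s falls and downward when s rises. Illustration with T unchanged and an assumed s_pre of 10%:

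| Assumed s_post | (1 - s_post)/0.90 | Apparent change |
|---|---|---|
| 0% | 1.00/0.90 = 1.111 | +11.1% |
| 5% | 0.95/0.90 = 1.056 | +5.6% |
| 10% | 0.90/0.90 = 1.000 | 0% |
| 15% | 0.85/0.90 = 0.944 | -5.6% |
| 20% | 0.80/0.90 = 0.889 | -11.1% |

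**4. Why a wider total alone is not enough.** Assumed counts per 100 episodes, as untreated non-sustained / treated / untreated sustained or VF, taking all treated episodes as sustained:

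| Case | Pre | Post | Category 2 | All episodes | Sustained VT/VF |
|---|---|---|---|---|---|
| A: s rises | 75/15/10 | 70/10/20 | 90 to 80 (-11.1%) | 100 to 100 (0%) | 25 to 30 (+20.0%) |
| B: s falls | 70/10/20 | 75/15/10 | 80 to 90 (+12.5%) | 100 to 100 (0%) | 30 to 25 (-16.7%) |
| C: s constant | 75/15/10 | 70/20/10 | 90 to 90 (0%) | 100 to 100 (0%) | 25 to 30 (+20.0%) |

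The totals are fixed at 100 by construction. The cases show only that neither category 2 nor a pooled total need track sustained episodes. In A, category 2 falls while sustained episodes rise.

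**5. Scope.** 6 period pairs × 3 analysis sets (retrospective, prospective, together) = 18 tabulations of category 2.

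**The case against.** A therapy-based count, plus a second count that adds non-sustained VT, can be a deliberate choice, and an operational definition is normally narrower than a general rationale. That stands to this extent: section 3.1 does not contradict the categories. But the plan gives no reason for leaving these episodes out.

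One could read untreated non-sustained VT as shorthand for all untreated VT. The text does not say so, and untreated VF would still be missing. Naming the device as the source of the counts does not widen the listed categories either.

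The comparison is within patient, no mechanism for a change in the omitted share is documented, and the 10% is assumed. All of this stands. A reader might infer that the VA result will be biased, or that the rule will hide a real rise in sustained arrhythmia. The documents support neither: they give no frequency of such episodes, and a constant share leaves the ratio for all episodes unbiased.

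A reader might also take the 18 comparisons as 18 formal tests. Section 5.3.2 commits only to tabulation.

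Finally, the device may report episodes by type, so the gap may lie in the grouping and not in data capture. That is possible. It would make the omission recoverable, but it does not change what the stated categories count.

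**Conclusion.** The gap holds on the text of 4.1 and 4.3, and no other section closes it. Followed literally, the plan counts short untreated VT and leaves out untreated sustained VT and untreated VF. For subjects without device therapy, that excludes every sustained VT and every VF.

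Size and direction cannot be derived from the documents. The ±11.1% range rests entirely on the assumed shares (10% before implant, 0% to 20% after) and an unchanged total.

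The reach is one of nine exploratory objectives, with up to 18 tabulations of category 2 and an optional test. It would be wrong to extend it to the main result: the hypothesis, the primary objective and the sample size of 77 in section 5.1 all concern AF burden. This is a minor point, worth correcting because correction is cheap.

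**What to change.** - In 4.1 and 4.3, redefine category 2 as all device-recorded VT and VF, treated or untreated, sustained or non-sustained.
- Add one tabulated line for sustained VT/VF regardless of therapy, since a pooled total can hide a change in these episodes.
- In 4.3, change the retrieval wording from VT to VA so that it matches 4.1. As written, only 4.1 supports retrieving VF as well.
- Optionally, report device type (ICD or pacemaker) with the VA counts, so that zeros in category 1 can be read correctly.

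If the omission is intended, the minimum is to say so, give the reason, and still add the sustained line.

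The cost is wording in two sections and one more table line, plus one descriptive variable if the option is taken. Section 4.1 already has VA episodes coming through the manufacturer. It is best settled before data entry: if the database fields follow the two present categories, the omitted episodes would have to be abstracted again, at up to 50 subsites. The downside is that the documents do not say whether each manufacturer's report labels untreated sustained episodes separately, and the added line depends on that.

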4.1.1 Study Duration

The study will last approximately 2 years to allow for enrollment.

